6.2.7. Other Displays

The following COVID-19 related displays will be provided.

- Summary of Subject Status and Subject Disposition by Relationship to COVID-19 Pandemic.
- Summary of Treatment Status and Reasons for Discontinuation of Study Treatment by Relationship to COVID-19 Pandemic
- Important Protocol Deviations by Relationship to COVID-19 Pandemic
- Proportion of Subject Visits Impacted by COVID-19 Pandemic
- Summary of Treatment Interruption Due to COVID-19 Pandemic

CONFIDENTIAL

205270

- Figure of Visits Impacted by COVID-19 Pandemic
- Listing of All Subjects with Visits and Assessments Impacted by COVID-19 Pandemic

7. EFFICACY ANALYSES

7.1. Primary Efficacy Analyses

The primary efficacy estimand is the effect of daprodustat treatment relative to placebo regardless of adherence to treatment, the use of non-randomized ESA medication for any reason including rescue therapy, or the use of blood transfusions, in patients defined by the inclusion/exclusion criteria and assuming patients do not die before the end of the EP.

The primary Hgb efficacy assessment is based on the central lab Hgb, Q². If central lab Hgb is missing then the data will be derived from Hemocue.

7.1.1. Endpoint / Variables

Mean change in Hgb between baseline and over the evaluation period (EP, mean over Week 24 and 28).

7.1.2. Summary Measure

Model-adjusted mean treatment difference (LS mean difference) in Hgb change between baseline and over the evaluation period.

7.1.3. Population of Interest

The target population is defined by the study's inclusion and exclusion criteria.

The analysis population included in the primary efficacy analyses will be based on the All Randomized (ITT) population, unless otherwise specified.

7.1.4. Strategy for Intercurrent (Post-Randomization) Events

The following are the intercurrent events for the primary efficacy analyses:

- Death prior to the end of the EP (i.e. before Week 28 visit)
- Randomized treatment discontinuation prior to the end of the EP
- Use of non-randomized ESA medications for any reason including rescue prior to the end of the EP
- Receipt of blood transfusions prior to the end of the EP

Except for the intercurrent event of deaths prior to the end of the EP, a treatment policy strategy will be used in which all scheduled Hgb data recorded during the EP (Weeks 24-28) will be included in the primary efficacy analysis, regardless of discontinuation of study medication due to any reasons, and regardless of receipt of non-randomized ESA medications for any reason including rescue, or blood transfusions. For deaths, a hypothetical strategy will be used as described in Section [7.1.5.1](#).

The following are causes of missing Hgb data affecting the primary efficacy endpoint that are not due to intercurrent events:

- Study withdrawal prior to the end of the EP
- Permanent switching from clinic visits to remote visits prior to start to EP
- Intermittent missing Hgb values at one or more visits with the EP

Missing data will be imputed as described in Section 7.1.5.1.

7.1.5. Statistical Analyses / Methods

Details of the planned displays are provided in [Appendix 10](#): List of Data Displays and will be based on GSK data standards and statistical principles.

Unless otherwise specified, endpoints / variables defined in Section 7.1.1 will be summarised using descriptive statistics, graphically presented (where appropriate) and listed.

7.1.5.1. Statistical Methodology Specification

| |
|---|
| Endpoint / Variables |
| 
 • Mean change in Hgb between baseline and over the evaluation period (EP, mean over Weeks 24 to 28) |
| Model Specification |
| 
 • The EP Hgb value will be defined as the mean of all available Hgb values (on and off-treatment) during the EP (Week 24 to Week 28 inclusive) • The ANCOVA model used to quantify the difference in mean Hgb change will adjust for the following baseline values: 
 ○ Treatment ○ Baseline Hgb (see Section 5.2) ○ Region (as randomized, see Section 5.3 & Section 5.4) |
| Multiple Imputation Analysis |
| 
 • Multiple imputation analysis will be performed using all available Hgb values (on and off-treatment) and conducted under a set of assumptions about missing Hgb values (see Section 10.6.3). 
 ○ For each of the missing dataset (out of the 200 imputed as indicated above), the missing scheduled Hgb values through Week 28 will be imputed based on the MNAR assumption and will be performed using PROC MI. The regression will have region, treatment, baseline Hgb, off treatment status, prior scheduled (possibly imputed) Hgb values as covariates (see Model Checking & Diagnostics, below). The seed for reproducibility is set to 205270. ○ Missing data will be considered MNAR and classified as either being on-treatment or off-treatment, with the former being imputed with only on-treatment data and the latter being imputed with only off-treatment data 
 ▪ Subsequent missing data will be classified as being on-treatment, if 
 • Patients who die, use non-randomized ESA Medication, Receipt of Blood Transfusions while on treatment • Study Drug Interruption (e.g. temporarily stopped trt due to COVID, then restarted) ▪ Subsequent missing data will be classified as being off-treatment, if 
 • Treatment discontinuation • Patients who die, use non-randomized ESA Medication, Receipt of Blood Transfusions after treatment discontinuation |

CONFIDENTIAL

205270

- The low and high cutoffs at Hgb values of 6 g/dL and 15 g/dL will be applied to all imputed Hgb values.
- EP Hgb values will be computed and compared across treatment groups using the co-primary ANCOVA model described above. Rubin's rules [Rubin, 1987] will be used to combine results of the imputed datasets using SAS PROC MIANALYZE procedure. As a result, a single estimated treatment difference and its standard error will be produced, with which a 95% CI will be calculated.

Model Checking & Diagnostics

- Distributional assumptions underlying the model used for analysis will be examined by obtaining a normal probability plot of the residuals and a plot of the residuals versus the fitted values (i.e. checking the normality assumption and constant variance assumption of the model respectively) to gain confidence that the model assumptions are reasonable.
- If there are any departures from the distributional assumptions, alternative models will be explored using appropriate transformed data.
- Models will be examined for treatment interactions with baseline Hgb and stratification factor
- Missing data imputation:
 - When imputing for each of the missing dataset (out of the 200), if there are error and or warning messages related to the by statement and/or regression model (e.g. not enough observations with the statement), try impute with randomized treatment, baseline Hgb, treatment status, prior scheduled (possibly imputed) Hgb values and region as covariates.
 - If there are no observed off-treatment Hgb values at a visit, the missing Hgb values at that visit will be imputed based on only the observed on-treatment Hgb values.

Model Results Presentation

- All available observed Hgb values (on and off-treatment) will be summarized using mean, standard deviation, minimum, P25, median, P75 and maximum at each visit by treatment group. In addition to scheduled visits, the baseline value and mean EP will be included (see Section 10.6.3). The summaries described above will be produced using the analysis defined Hgb.
 - This display will be repeated for visits up to and including Week 28, using the data used for the primary Hgb analysis (i.e., including imputed values).
- All available observed Hgb change from baseline values (on and off-treatment) will also be summarized using mean, standard deviation, minimum, P25, median, P75, and maximum at each post-baseline visit, including the mean EP (see Section 10.6.3).
 - This display will be repeated for visits up to and including Week 28, using the data used for the primary Hgb analysis (i.e., including imputed values).
- The number and percentage of subjects with imputed data in the primary Hgb analysis will be provided by treatment group. The number and percentage of subjects by reason for data imputation will be provided. Reasons include: death before Week 24, death during Week 24 – 28, investigator site closed before Week 24, investigator site closed during Weeks 24-28, lost to follow-up before Week 24, lost to follow-up during Week 24 – 28, consent withdrawn before Week 24, consent withdrawn during Week 24 – 28, and other monotone missing Hgb values. Subjects will be further classified as either having observed both scheduled EP Hgb values, Having observed a partial schedule of EP Hgb values, having observed no scheduled EP Hgb values with at least one unscheduled EP Hgb value, or having observed no EP Hgb values, scheduled or unscheduled. For subjects with partial scheduled EP Hgb values, the amount of imputed data (1 scheduled Hgb values missing) will be summarized. For subjects with partial scheduled EP Hgb values and a monotone imputed data pattern, the reason for the monotone imputed scheduled EP Hgb values will be provided. Reasons include: death during Week 24-28, investigator site closed during Weeks 24-28, lost to follow-up during Week 24 – 28, consent withdrawn during Week 24 – 28, and other monotone imputed Hgb values. And for summaries of the amount of missing scheduled EP Hgb values, the presence or absence of additional unscheduled EP Hgb values will be summarized.

CONFIDENTIAL

205270

- The least square (LS) mean estimates and standard errors by treatment group, LS mean difference, two-sided 95% CI and one-sided superiority p-value for the difference in the primary Hgb endpoint between the daprodustat and placebo arms from the ANCOVA model will be presented. The number of subjects contributing to the analysis and the associated mean and standard deviation of the baseline and EP Hgb values will also be displayed with the results of the ANCOVA model.
- All available mean Hgb values (on and off-treatment) will be displayed graphically for each scheduled study visit using a line plot. The line plot of mean values and the 95% CI by time will include horizontal reference lines to depict the hemoglobin analysis range (11-12 g/dL), vertical reference lines to identify the EP (weeks 24-28), and the number of subjects by treatment group contributing to each mean value.
- All available Hgb change from baseline values (on and off-treatment) will be displayed graphically for each scheduled study visit using a line plot. The line plot of mean values and the 95% CI by time will include vertical reference lines to identify the EP (Weeks 24-28), and the number of subjects by treatment group contributing to each mean value.
- A listing of all hemoglobin values will be provided, including treatment, site ID, unique subject ID, subject ID, visit, assessment date, select demographic information and central laboratory and HemoCue Hgb values.

Model Results Interpretation

Superiority will be established if the one-sided p-value is less than 0.025.

Subgroup Analyses

- Subgroup analysis will be performed using all available Hgb values (on and off-treatment) and separately using evaluable Hgb values only (see Section 10.6.3).
- Subgroup analysis details are discussed in Section 5.4.
- The ANCOVA model used to quantify the difference in mean Hgb change will adjust for the following baseline values:
 - Treatment
 - Baseline Hgb (see Section 5.2)
 - Region (as randomized, see Section 5.3 & Section 5.4)
 - Subgroup
 - Subgroup * treatment interaction term

Supportive Analyses

- A supportive analysis using while alive and on treatment strategy (on-drug analysis) will be considered. In this analysis, the EP Hgb will be determined using evaluable Hgb values (Section 10.6.3). Hgb values collected after IP discontinuation, or within 8 weeks following a red blood cell transfusion, a whole blood transfusion, or a nonrandomized ESA treatment would be irrelevant to the analysis, since they are not of interest in this estimand.

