7.3. Method of Treatment Assignment

- Subjects will be stratified by region (Section 12.8 Appendix 8). Region at study entry is considered a stratification factor that is potentially prognostic of study endpoints. Following stratification all participants will be centrally randomized in a 1:1 fashion to receive either oral daprodustat or oral placebo.
- Once a randomization number has been assigned by the IRT system, it must not be re-assigned
- Study treatment will be dispensed at the study visits summarized in the SoA (Section 2).
- Returned study treatment should not be re-dispensed to the participants.

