10. STATISTICAL CONSIDERATIONS AND DATA ANALYSES

10.1. Primary Hypothesis

The primary Hgb efficacy objective will assess the estimand defined as the comparative treatment effect in mean Hgb change between baseline and evaluation period (EP, i.e., week 24 to week 28 inclusive) in all randomized participants; defined as those who remain in follow-up throughout the period of stabilization and have at least one Hgb assessment during the EP regardless of adherence to study treatment. The analysis will test whether daprodustat is superior to placebo according to the following statistical hypotheses:

- **Null:** The difference in mean change in Hgb between baseline and EP, between treatment arms (daprodustat-placebo), is less than or equal to 0 g/dL.
- **Alternative:** The difference in mean change in Hgb between baseline and EP between treatment arms (daprodustat-placebo), is greater than to 0 g/dL.

Statistical significance will be assessed at the one-sided 2.5% level. An analysis of covariance (ANCOVA) model including the randomization stratification factor, baseline hemoglobin and treatment will be used to obtain a point estimate and the two-sided 95% CI for the treatment difference (daprodustat-placebo) and generate the one-sided p-value for the superiority test. Superiority will be established if the one-sided p-value is less than 0.025.

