10.2. Sample Size Determination

10.2.1. Sample Size Assumptions

The sample size of this study has been primarily determined in order to achieve sufficient power for the principal secondary endpoint SF-36 vitality sub-score, since the anticipated effect size of this endpoint is less than that for the primary endpoint.

Approximately 600 participants are planned to be randomized (300 per arm) to receive daprodustat or placebo, who will be treated to achieve and maintain Hgb between 11 and 12 g/dL. Under the assumption that up to 10% of participants will withdraw from the study before Week 24 (start of EP), 600 randomized participants will result in at least 540 evaluable participants.

For the primary endpoint, the expected difference in mean Hgb change from baseline and the EP, between arms, is 1.0 g/dL and the anticipated between participant standard deviation (SD) is 1.5 g/dL, based on historical rhEPO trials and daprodustat clinical trial experience to date. The planned study size provides more than 99% power for superiority. In addition, it is anticipated that the smallest difference in mean Hgb change between arms that would meet the statistical criterion for superiority would be 0.25 g/dL.

For the first principal secondary endpoint of % of participants having a Hgb increase of ≥ 1.0 g/dL from baseline to EP, 540 evaluable participants provides $>90\%$ power to detect a 20% difference between daprodustat and placebo, assuming 30% of placebo arm participants will have a Hgb increase of ≥ 1.0 g/dL. In that case the smallest difference between daprodustat and placebo that would meet the statistical criterion for superiority would be 8%.

For the second principal secondary endpoint of mean change in SF-36 vitality sub-score between baseline and week 28, 540 evaluable participants provides for 79% power to detect a difference between arms under the assumption of a between treatment effect of 5 points in favor of daprodustat and a within-group standard deviation of 21 points. Prior research has determined that anemia is associated with a difference of 5.4 points from baseline for SF-36 vitality scores (Bjorner, 2007). It is expected that the smallest difference between arms that would meet the statistical criterion for superiority in this principal secondary endpoint is 3.5 points.

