10.4. Key Elements of Analysis Plan

10.4.1. Primary Analyses

Mean change in Hgb between baseline and EP (week 24 to week 28 inclusive): The primary efficacy estimand is to compare the effect of treatment for the evaluation of mean change from baseline in Hgb during the 4 week EP in all ITT participants with at least one Hgb during the EP. The ITT analysis of this endpoint will include all on and off treatment Hgb values of the ITT population, including values taken after rescue and IP discontinuation. The analysis will use an ANCOVA model. For each participant, the baseline Hgb will be the value obtained on Day 1, prior to taking randomized treatment, and Hgb during EP will be determined by calculating the mean of all available Hgb values between week 24 to week 28 inclusive regardless of the use of rescue medication

or adherence to randomized treatment. The ANCOVA model will include the randomization stratification factor, baseline Hgb and treatment. It will provide a point estimate and two-sided 95% CI for the treatment effect, together with the one-sided p-value. There will be no imputation for missing data.

Sensitivity Analysis: A sensitivity analysis that considers an “on-drug” efficacy estimand will be conducted. In this analysis, only Hgb values measured while the participant was taking randomized study medication will be included. Missing Hgb values will be imputed based on the reasons of missing. Full details will be provided in the RAP.

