- Subjects with scheduled off-treatment SF-36 data will be imputed assuming they were on treatment.
 - The low and high cutoffs at SF-36 values of 0 and 100 for traditional scoring and 22.89 and 70.42 for norm-based scoring will be applied to all imputed SF-36 values.
 - For the SF-36 principle secondary endpoint supportive analysis imputing subjects who have remote/over the phone SF-36 visits during Week 28 and those subjects who were treatment interrupted prior to their Week 28 visit will be performed using on treatment SF-36 values and conducted under a set of assumptions about missing sf-36 values (see Section 10.6.3). This is a similar imputation strategy as outlined above but will be based on on-treatment SF-36 values and consider those subjects who completed SF-36 remotely/over the phone or who were treatment interrupted prior to Week 28 as missing.

Supportive Analyses

- For the first principal secondary endpoint, a supportive analysis using while alive and on treatment strategy (on-drug analysis) will be performed using a Cochran-Mantel-Haenszel (CMH) chi-squared test, adjusting for treatment, and region (see Section 5.3), will be used to make comparisons between the treatment groups. No imputation will be performed for this analysis.
- For the second principal secondary endpoint, a treatment policy strategy (on and off treatment) analysis will be performed using an ANCOVA model including all participants with on and off treatment values, including factors for baseline score, treatment, and region. This will be done for both traditional and norm-based scoring. No imputation will be performed for this analysis.
- For the second principal secondary endpoint, a while alive and on treatment strategy (on treatment only) analysis will be performed using an ANCOVA model including all participants with on treatment values, excluding subjects who IP discontinue/rescue, including factors for baseline score, treatment, and region. This will be done for both traditional and norm-based scoring. No imputation will be performed for this analysis.

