10.6.3. Efficacy

| Hemoglobin Values |
|--|
| Central Laboratory and HemoCue Hgb Values |
| 
 • When source of Hgb measurement is not specified: 
 ○ For reporting purposes, central laboratory Hgb values will be used, unless otherwise specified. However, if a central laboratory Hgb value is missing, a corresponding non-missing HemoCue Hgb value will be used. • Multiple HemoCue Hgb values at a single visit: 
 ○ The dose adjustment algorithm will require sites to obtain two HemoCue Hgb values at some visits. In the case where two HemoCue Hgb values are obtained at a visit, the average of the two measurements, which will be rounded to the nearest 10th decimal place, should be used as the HemoCue Hgb value for that visit. |

CONFIDENTIAL

205270

| |
|---|
| Hemoglobin Values |
| Evaluable Hemoglobin Values |
| 
 Evaluable Hgb values are on-treatment Hgb values (see Section 10.4.1) that are not taken within the 8 weeks following a red blood cell transfusion, a whole blood transfusion, or a nonrandomized ESA treatment which occurs on or after the randomization date. |
| Evaluation Period (EP) Hemoglobin Value for Primary Hgb Analysis |
| 
 For each participant, the mean of all available (on and off treatment) Hgb values for Week 24 through Week 28, inclusive, including any unscheduled Hgb values that were taken during this time period. |
| Evaluation Period (EP) Hemoglobin Value for On-drug Hgb Supportive Analysis |
| 
 For each participant, the mean of all evaluable Hgb values for Week 24 through Week 28, inclusive, including any unscheduled Hgb values that were taken during this time period. |
| Imputed Hemoglobin Values |
| 
 For each missing value between baseline to Week 28 (inclusive), 200 imputed values will be generated using the multiple imputation method (see Section 7.1.2). The average of these 200 imputed values will be used as the value for this missing value in the summary tables and figures. For the primary efficacy Hgb analysis and the corresponding subgroup analyses using all available observed and imputed Hgb values (on and off-treatment), Rubin's rules [Rubin, 1987] will be used to combine results of the imputed datasets using SAS PROC MIANALYZE procedure. |
| Time In Range |
| Time in Range During the EP |

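### The on-drug Hgb supportive analyses lose the protocol's reason-based imputation without a log entry and keep only participants with evaluable Week 24–28 values, so they condition on a post-randomization outcome and do not match their while-alive-and-on-treatment label

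*SAP*

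**What the plan says.** **Protocol 10.4.1 (Sensitivity Analysis).** The on-drug analysis uses only Hgb measured while the participant was taking study medication. It then adds: "Missing Hgb values will be imputed based on the reasons of missing". Full details are deferred to the Reporting and Analysis Plan, which is the SAP.

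**SAP 7.1.5.1 (Supportive Analyses).** The analysis is described as a while-alive-and-on-treatment strategy that will be considered. On the outcome it says: "In this analysis, the EP Hgb will be determined using evaluable Hgb values". SAP 10.6.3 defines that outcome as "For each participant, the mean of all evaluable Hgb values for Week 24 through Week 28, inclusive", with unscheduled values in the window added. Evaluable means on treatment and not within 8 weeks after a transfusion or a non-randomized ESA.

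**Imputation.** None is specified for this analysis. SAP 10.6.3 applies the 200 imputations to the primary Hgb analysis and its subgroup analyses on all on- and off-treatment values. The on-drug version of the ≥1.0 g/dL responder endpoint (SAP 7.2.5.2) states that nothing is imputed. The evaluable-Hgb subgroup analysis is Table 2.10 and the on-drug analysis itself is Table 2.11.

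**Change log.** The only row of SAP Table 1 on how an Hgb analysis handles missing data concerns the primary analysis.

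**Why participants leave treatment.** Protocol 7.7.2, Table 7, requires permanent discontinuation of randomized treatment when Hgb stays low under the rescue algorithm.

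**The concern.** A participant who stops treatment before Week 24 has no evaluable value in Weeks 24–28 and so no outcome for the ANCOVA. Because Table 7 ties stopping to low Hgb, those removed are selected partly on the outcome, and probably more often on placebo. The comparison is then between participants who stayed on treatment, not between randomized groups.

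The label does not fit either. A while-on-treatment strategy summarises each participant's response up to stopping. Here the earlier on-treatment values of early stoppers are discarded along with the participant.

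What is at stake is interpretation. A gap between this result and the primary one would read as a difference between estimands, when part of it would be selection. The subgroup and responder versions inherit the problem.

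**Working it through.** **1. Planning inputs and the plan's own figure.** From Protocol 10.1, 10.2.1 and 7.3: "Statistical significance will be assessed at the one-sided 2.5% level"; "the expected difference in mean Hgb change from baseline and the EP, between arms, is 1.0 g/dL"; "the anticipated between participant standard deviation (SD) is 1.5 g/dL"; 1:1 allocation with 270 evaluable per arm. The smallest significant difference is 1.96 × 1.5 × √(2/270) = 0.253 g/dL. The protocol states 0.25, so it reproduces. Neither document gives a figure for the on-drug analysis.

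**2. Illustrative model.** Protocol 10.2.1 assumes that 30% of placebo participants rise by ≥1.0 g/dL. With a normal distribution and SD 1.5, the placebo mean change is 1.0 − 1.5 × 0.5244 = 0.213, and daprodustat is 1.213. The protocol's values are for endpoints that include post-rescue Hgb. Using them as on-drug values is an assumption, as is a baseline uniform on 8.5–10.0 g/dL.

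**3. Effect of dropping early stoppers.** For each arm, let m be the mean change. Let L be the share whose evaluation-period (EP) Hgb would be below 8.5 g/dL on continued treatment, and c the mean change in that group. Let q be the fraction of that group stopped before Week 24. With a = (8.5 − b − m)/1.5 averaged over baseline b:

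- L = mean of Φ(a): 0.269 placebo, 0.104 daprodustat.
- L·c = mean of mΦ(a) − 1.5φ(a): −0.418 placebo, −0.135 daprodustat.
- Mean change among those retained = (m − q·L·c)/(1 − q·L).

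| q (assumed) | Removed, placebo / daprodustat | Retained mean, placebo / daprodustat | Difference |
|---|---|---|---|
| 10% | 2.7% / 1.0% | 0.262 / 1.239 | 0.98 |
| 25% | 6.7% / 2.6% | 0.340 / 1.280 | 0.94 |
| 50% | 13.4% / 5.2% | 0.488 / 1.351 | 0.86 |
| 75% | 20.2% / 7.8% | 0.659 / 1.426 | 0.77 |
| 100% | 26.9% / 10.4% | 0.863 / 1.505 | 0.64 |

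The true on-drug difference is 1.00 throughout. With baseline uniform on 9.0–10.5 the differences run from 0.98 to 0.73. A cruder version, with zero placebo change and everyone below a fixed cut removed (8% to 37% of placebo), gives 0.53 to 0.83. I do not rest on it.

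**4. Responder endpoint.** I read no imputation as removing participants without a value from the denominator. A rise of ≥1.0 g/dL from a baseline of at least 8.5 puts Hgb above 8.5, so no responder is removed. The placebo rate becomes 0.30/(1 − 0.269q): 31% at q = 10%, 35% at 50%, 41% at 100%. The relative response rate is multiplied by (1 − 0.269q)/(1 − 0.104q), which is 0.98 at q = 10% and 0.731/0.896 = 0.82 at q = 100%.

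**5. Visit-level check.** I simulated stopping at Hgb <7.5 g/dL, or <8.5 at three consecutive visits, and analysed by ANCOVA. Mean baseline 9.3 g/dL, visit correlation and ramp-up were assumed; the symptom criterion and the iron step were left out. In the base case 21% of placebo and 7% of daprodustat had no evaluable EP value. The evaluable-only estimate was 0.71 against 0.99 for all participants on drug. Other visit-level runs gave 0.75 to 0.90 for evaluable-only, and about 1.00 after same-arm imputation from prior on-treatment Hgb.

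**6. Comparison with the treatment-policy result.** In the same base case the treatment-policy estimate was 0.75, 0.68, 0.54 or 0.47 when rescued Hgb was set to 9.0, 9.5, 10.5 or 11.0. The evaluable-only 0.71 lies below the first and above the other three.

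**The case against.** Several points on the other side stand.

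- **Another on-drug analysis exists.** SAP 7.3.2.1 plans an MMRM of Hgb change at Week 28 on evaluable values (Table 2.40), treating participants who discontinue treatment as missing at random. It keeps early stoppers' on-treatment values. A likelihood-type fit to all on-treatment visits gave 0.98 to 1.01 in simulation. A reader might infer that the on-drug EP analysis is the only look at Hgb under a second estimand; it is not. The MMRM does not, however, cover the EP mean, the Table 2.10 subgroups or the responder endpoint.
- **Direction.** A reader might infer that the method simply shrinks the effect. Step 6 shows that it can exceed the primary estimate, because rescue raises placebo Hgb. Against the protocol's own analysis the direction cannot be stated, since its reason-based rule was never written.
- **Size.** Stopping rates by arm appear nowhere. Protocol 5.4 expects few drop-outs for lack of effect, which points to the top rows of the table.
- **SF-36.** The SF-36 supportive analysis is worded "including all participants with on treatment values, excluding subjects who IP discontinue/rescue", which invites the same criticism. But Protocol 10.4.2.1 itself planned on-treatment SF-36 values only, with no imputation stated. The SAP made an imputed analysis the principal one, logged that, and kept this version as supportive. It is not an unlogged loss, and the case for changing it is not made.
- **Silence.** For the on-drug Hgb change analysis the SAP does not rule imputation out. But the protocol promised the details there, so the omission is itself the gap.

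**Conclusion.** The point holds for the on-drug Hgb analyses: the EP change, its evaluable-Hgb subgroups and the ≥1.0 g/dL responder version. The protocol's reason-based imputation is absent and its removal unlogged. As written, these analyses keep only participants with evaluable EP Hgb and so condition on a post-randomization outcome.

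Relative to the on-drug effect in all randomized participants, the expected bias is towards no difference, provided rescue is more common on placebo. The illustrative size is 0.64 to 0.98 g/dL against 1.00. It rests on assumed stopping fractions of 10% to 100% of low-Hgb participants, normality, an assumed baseline distribution, and planning values borrowed from a treatment-policy endpoint.

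A reader might infer that the trial's main conclusion is at risk. The documents do not support that: the primary analysis includes all randomized participants, and the on-drug analyses sit outside the testing hierarchy in SAP 5.5. This is a could-do change.

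**What to change.** In SAP 7.1.5.1, for the on-drug analysis:

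1. Set non-evaluable Hgb to missing and impute through Week 28 with the existing 200-imputation code, using on-treatment data from the same arm and prior Hgb.
2. Either state how the rule varies by reason for missingness, or record in SAP Table 1 that reason-based imputation was replaced. A single same-arm rule does not by itself deliver what Protocol 10.4.1 describes.
3. Label the estimand hypothetical: the effect had participants remained on treatment.
4. Derive the on-drug ≥1.0 g/dL responder endpoint and the evaluable-Hgb subgroup analyses from the same imputed data.
5. Keep the present versions as extra displays, titled as participants with evaluable EP Hgb and cross-referenced to the evaluable-Hgb MMRM in SAP 7.3.2.1.

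The SF-36 supportive analyses stay as they are. The cost is SAP wording and a rerun of existing code, with no new data. The downside is that the on-drug result will rest on a stated imputation assumption.
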